6.6.1. Primary Efficacy Analysis

The primary efficacy variable is defined as HiSCR75, the proportion of subjects who achieve at least a 75% reduction from baseline in the total AN count, with no increase from baseline in abscess or draining fistula count at Week 16 (comparing to baseline).

For Part B, the statistical null and alternative hypotheses to be used to assess the primary objective are:

> H₀: $\pi_{ABY} - \pi_{PBO} = 0$ H_A: $\pi_{ABY} - \pi_{PBO} \neq 0$

where π_{ABY} and π_{PBO} are the proportion of subjects achieving HiSCR75 at Week 16 among subjects randomly assigned to receive izokibep and placebo, respectively. One set of hypotheses will be tested for each dosing frequency of izokibep.

The treatment policy strategy approach for the estimand will be used in general, so subjects will be included using observed data at Week 16 regardless of treatment compliance, use of rescue medications or procedures except as noted below, or any other protocol deviations. Subjects with missing HiSCR75 assessments at Week 16 will be imputed as non-responders (non-response imputation or NRI). A composite strategy will be used for intercurrent events of receiving oral antibiotic therapy that could affect HS. A list of all oral antibiotic therapy that results in such imputation will be finalized after review of all oral antibiotic therapy received by any subject and before unblinding of the study and will include tetracycline, clindamycin, and possibly other products. Such subjects will be imputed using NRI. The Page 37 of 75 Final, Version 3.0, 03APR2024

ST-AD-008 version 06

number of subjects imputed with NRI will be tabulated with reasons for imputation at Week 16. Additionally, any lesions that received lesional incision and drainage or intralesional steroid injection will be counted as continuing to exist in the AN count, even if fully healed, at all later timepoints.

The null hypothesis of equal response rates will compare each dosing regimen of izokibep to the combined placebo group.

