 - Descriptive MMRM analyses will be performed by randomized treatment group, for change from baseline of IHS4 score and draining fistula count at Week 24 and Week 32. The change from baseline value will be used as the response variable, with baseline value, visit week, treatment, and treatment * visit week interaction included as predictors in the model. Estimated LSMean change from baseline, corresponding SE values, and 95% confidence intervals will be presented in the table summaries.

- The subgroup of subjects who were responders at Week 16 by AN count of 0, 1, or 2 (among those with Hurley stage II at baseline) will also be evaluated at Week 24 and Week 32 in the same manner as described for HiSCR75 responders.
- The subgroup of subjects who were non-responders at Week 16 by HiSCR75 will also be evaluated at Week 24 and Week 32 in the same manner as described for HiSCR75 responders.
- The subgroup of subjects who were non-responders at Week 16 by AN count of 0, 1, or 2 among those with Hurley stage II at baseline will also be evaluated at Week 24 and Week 32 in the same manner as described for the HiSCR75 responders.
- McNemar test will be used to evaluate the relationship between HiSCR75 response at Week 16 vs various response criteria at Week 32. P-values will be provided for descriptive purposes. The following response criteria at Week 32 will be used for this analysis:
 - o HiSCR75
 - o HiSCR90
 - HiSCR100
 - o HiSCR50
 - $\circ \quad \text{AN count of } 0, 1, \text{ or } 2$
- McNemar test will be used to evaluate the relationship between "AN count of 0, 1, or 2" response at Week 16 vs various response criteria at Week 32. P-values will be provided for descriptive purposes. The following response criteria at Week 32 will be used for this analysis:
 - o HiSCR75
 - HiSCR90
 - HiSCR100
 - HiSCR50
 - AN count of 0, 1, or 2

The following analyses will be done (by randomized treatment groups) for only the FAS subjects randomized to placebo who had least one dose of izokibep in Period 2 of the study AND who had a total AN count of \geq 5 at Week 16 and HS lesions present in at least 2 distinct anatomic areas (to correspond to the inclusion criteria), to address the question of how subjects respond to izokibep after 16 weeks of placebo, when they still meet original eligibility criteria:

- The baseline characteristics summary described in section 6.4.2 will be repeated for this analysis set at Week 16.

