- The following binary endpoints will be analyzed analogously to the primary endpoint by randomized treatment group. The number and proportion of subjects for binary endpoints in each treatment group, 95% CI without strata calculated using asymptotic Wald method will be reported as well.
 - HiSCR50, HiSCR75, HiSCR90 and HiSCR100 calculated with respect to Day 1 at weeks 24 and 32;

HiSCR50, HiSCR75, HiSCR90 and HiSCR100 calculated with respect to Week 16 at weeks 24 and 32

HiSCR50/75/90/100 with respect to Week 16 is defined as meeting all three criteria below:

- (AN count at Week 16 AN count at current visit) / AN count at Week 16 \times 100% \geq 50/75/90/100%
- Abscess count at Week $16 \ge$ abscess count at the current visit
- Draining fistula count at Week 16 ≥ draining fistula count at the current visit
- AN count of 0, 1, or 2 at weeks 24 and 32 among subjects with baseline Hurley Stage II;
- AN count of 0, 1, or 2 at weeks 24 and 32 among subjects with Week 16 Hurley Stage II;
- HS flares from week 16 through 32, where HS flare is defined as proportion meeting the following two criteria at any assessment after Week 16 and at or before Week 32:
 - (AN count at current visit- AN count at Week 16) / AN count at Week $16 \times 100\% \ge 25\%$
 - AN count at current visit- AN count at baseline ≥ 2
- IHS4-55 response rates at weeks 24 and 32;
- Draining fistula count of 0 at weeks 24 and 32
- Proportion with at least 3 points reduction from baseline in NRS in Patient Global Assessment of Skin Pain at its worst, among subjects with Week 16 NRS ≥ 4, at weeks 24 and 32
- Descriptive MMRM analyses will be performed by randomized treatment group, for the continuous endpoints described below. The measured value at the visit will be used as the response variable, with visit week, treatment, and treatment * visit week interaction included as predictors. The model will include all visits from Day 1

through Week 32. Estimated LSMean, corresponding SE values, and 95% confidence intervals will be summarized. Line plots by treatment group will be produced:

- NRS Patient Global Assessment of Skin Pain (WORST). To maintain consistency between all visits, only the score collected on the visit day will be used for this analysis.
- Draining fistula count, Modified Sartorius Score, IHS4 Score, HS-PGA score, all HADS scores (Total, Anxiety, Depression), EQ-5D Utility Score and DLQI Total Score.

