Appendix 1: Document History

Appendix 2: End Points Definitions and Scoring Method Modified Sartorius Score⁸

The modified Sartorius score includes an assessment of the anatomical regions involved, the numbers and scores of lesions for each region, the longest distance between 2 relevant regions (or size of a single lesion), and whether all lesions are separated by normal skin (yes or no). The detailed scoring is as following:

Each region will score as:

Item No	Items	Scoring Rules	Points	Score:
1	Anatomical region	If the region is affected	3	
		If the region is not affected, the score for that region is 0, and no further calculations are needed for the region. If the region is affected, the following are added in addition to the 3 points for the region in line 1 above.		
	For each affected region:			
2	Nodules (Inflammatory)	Count from this region	1	$1 \times \text{count}$
3	Fistulae (Draining only)	Count from this region	6	$6 \times \text{count}$

4	Longest distance between two relevant lesions within a region or size of the lesion if single	< 5 cm	1	
		5 - 10 cm	3	
		> 10 cm	9	
5	Lesions separated by normal skin?*	Yes	0	
		No	9	
	Score for the region			Sum of above

* If Lesions separated by normal skin = "No" and/or Hurley Stage = "STAGE III" then 9 points is added for the region.

Score for each region is (if the region involved) = $3 + (number of inflammatory nodule) \times 1$ + {(number of draining fistula) × 6 + {0 < (The longest distance between two relevant lesions [or size of lesion if single]) <5} × 1+ {5≤(The longest distance between two relevant lesions [or size of lesion if single]) ≤ 10} × 3 + {(The longest distance between two relevant lesions [or size of lesion if single]) > 10} × 9 + (all lesions separated by normal skin = Yes or Hurley Stage = "STAGE III") × 9

Modified Sartorius score is the sum of the score of each region. Any region with no involvement will have a score of zero for purposes of calculating the modified Sartorius score.

A region is considered "affected" if any of the following conditions are true:

- Abscess Count > 0 OR
- Any "Interventions needed" questions response = YES
- Any "Interventions needed DATE" question is not missing.
- Any "How many lesions had intervention" question > 0
- Any "How many lesions had intervention AND are no longer present" > 0
- Non-draining fistula count > 0
- Draining fistula count > 0
- Non-inflammatory nodule count > 0

- Inflammatory nodule count > 0
- Hypertrophic scar > 0

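### In the placebo-switcher analysis, HiSCR from Week 16 still counts lesions treated and healed before Week 16, which puts HiSCR100, and HiSCR90 at lower counts, out of reach for the subjects who carry them

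*SAP*

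**What the plan says.** SAP 6.6.7 plans a set of summaries in placebo subjects who received izokibep in Period 2, had an AN count of at least 5 at Week 16 and had lesions in at least two areas. Its purpose is "to address the question of how subjects respond to izokibep after 16 weeks of placebo", in subjects who would still qualify for the trial. Among the endpoints are "HiSCR50, HiSCR75, HiSCR90 and HiSCR100 calculated with respect to Week 16 at weeks 24 and 32", with a definition of their own: "HiSCR50/75/90/100 with respect to Week 16 is defined as meeting all three criteria below". The criteria replace the baseline AN, abscess and draining fistula counts by the Week 16 counts. Of the method the SAP says: "The following binary endpoints will be analyzed analogously to the primary endpoint by randomized treatment group".

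The rule for treated lesions stands elsewhere. In SAP 6.6.1, "any lesions that received lesional incision and drainage or intralesional steroid injection will be counted as continuing to exist in the AN count", and this holds "even if fully healed, at all later timepoints". SAP 2.4 builds the same rule into the HiSCR definition by including treated lesions that have gone, and protocol 9.3.2 does so for the AN count. Protocol 6.8.2.5 tells sites to record a treated lesion as permanently present from the intervention date. The same section allows two interventions up to the Week 16 visit and takes a subject who needs more off study drug.

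SAP 6.6.7 contains no rule that resets the count at Week 16.

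**The concern.** With a Day 1 reference, carrying a treated lesion forward has a clear purpose: a procedure after baseline should not be credited to the study drug. With a Week 16 reference that purpose is gone for lesions treated and healed earlier. The procedure and the healing both came before the new reference and before the first izokibep dose, so there is no credit to deny. The rule only adds a fixed number to both counts that izokibep cannot reduce.

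Two things follow. The percentage reduction is capped below 100% in any subject who carries such a lesion, so the higher HiSCR levels can be out of reach however well the subject responds. And a subject with fewer than five live lesions can enter a set meant to mirror the original entry criterion, which was applied at screening and Day 1, before any on-study intervention.

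**Working it through.** The plan states no figure on this point, so there is none to reproduce. The check is exact arithmetic.

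**Inputs**
- N: the AN count at Week 16 as the plan counts it. The entry rule in SAP 6.6.7 gives N ≥ 5.
- m: distinct abscesses or inflammatory nodules treated before Week 16 and already healed at Week 16. Protocol 6.8.2.5 allows two interventions, so m is 0, 1 or 2. Two interventions on one lesion give m = 1. A treated draining fistula is not part of AN and does not enter m.
- c: live AN lesions at the later visit.

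**Formula.** As written, the Week 16 count is N and the later count is c + m. The reduction is (N − c − m)/N. With every live lesion cleared (c = 0), the maximum is (N − m)/N.

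| N | Maximum, m = 1 | Maximum, m = 2 |
|---|---|---|
| 5 | 80.0% | 60.0% |
| 6 | 83.3% | 66.7% |
| 7 | 85.7% | 71.4% |
| 8 | 87.5% | 75.0% |
| 9 | 88.9% | 77.8% |
| 10 | 90.0% | 80.0% |
| 19 | 94.7% | 89.5% |
| 20 | 95.0% | 90.0% |

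**Against the thresholds**
- HiSCR100: unreachable at every N when m ≥ 1.
- HiSCR90: unreachable for N = 5 to 9 when m = 1, and for N = 5 to 19 when m = 2.
- HiSCR75: always reachable when m = 1, since the lowest maximum is 80.0%. Unreachable when m = 2 only at N = 5, 6 or 7. At N = 8 the maximum is exactly 75.0%.
- HiSCR50: always reachable, since the lowest maximum is 60.0%.

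**Short of the cap.** The carried lesions also make a reachable level harder to meet. With N = 10, m = 2 and one live lesion left, the plan gives (10 − 1 − 2)/10 = 70.0%. On live lesions it is (8 − 1)/8 = 87.5%.

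**Entry rule.** The live count at Week 16 is N − m. At N = 5 and m = 2 a subject with 3 live lesions enters. If the rule used live lesions, entry would need N ≥ 6 (m = 1) or N ≥ 7 (m = 2). So of the three counts at which HiSCR75 is blocked, N = 5 and N = 6 belong to subjects who are in the set only because of carried lesions.

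**With healed lesions left out of both counts.** The reduction becomes (N − m − c)/(N − m), whose maximum is 100% for every subject. For example, N = 7 with m = 2 and all live lesions cleared moves from 71.4% to 100%.

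**The case against.** The strongest reply is that this is one general counting rule applied consistently, that it errs on the conservative side, and that little hangs on it. The analysis is an additional Period 2 summary in a post-randomisation subset without a concurrent control. It lies outside the alpha-controlled sequence in SAP 6.6, which also says that Period 2 in general carries no hypothesis tests. Other endpoints are reported for the same set. All of this stands and limits the weight of the point. It does not remove it, because the capped levels do not answer the question the section sets itself.

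One could also read the reference to the primary endpoint as covering the statistical method alone. That does not help: the AN definition in SAP 2.4 applies to all HiSCR levels, and the sites' counts already carry the treated lesions.

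A reader might infer that HiSCR75 is often blocked, or that anyone with a Period 1 intervention is bound to fail the higher levels. The documents do not support either. One carried lesion never blocks HiSCR75, and HiSCR90 is reachable from N = 10 (m = 1) or N = 20 (m = 2). A treated lesion still present at Week 16 is a proper part of the Week 16 burden.

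A last objection concerns the remedy. Dropping every lesion treated before Week 16 and absent later would credit izokibep with one that was injected or drained shortly before Week 16, was still there at Week 16, and then healed. That is right, and the fix must be limited to lesions already gone at Week 16.

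**Conclusion.** The point holds for the Week 16-referenced HiSCR endpoints in SAP 6.6.7 and for the AN ≥ 5 entry rule of that set. HiSCR100 is impossible for every subject who carries a healed abscess or nodule, HiSCR90 is impossible over the lower counts given above, and HiSCR75 is blocked only in a narrow corner. The cap works downward only.

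How many subjects it touches is unknown. The documents give neither an intervention rate nor the distribution of Week 16 counts. A reader might apply an assumed rate to all placebo subjects, about 57 (two groups of 28 to 29), but that overstates the number, because the set keeps only those dosed in Period 2 who meet the Week 16 lesion criteria. For scale, results are given by randomised group: one subject wrongly held as a non-responder moves a rate by 1/29 to 1/28, or 3.4 to 3.6 percentage points, if the whole group entered, and by more in the smaller set.

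Nor should anyone infer that the primary or secondary results are affected. They use Day 1 as reference, where the rule does its job.

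The conclusion assumes that the general rule applies in SAP 6.6.7, as the text implies, and that the two-intervention limit was followed.

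**What to change.** In SAP 6.6.7, for the Week 16-referenced HiSCR endpoints and the AN ≥ 5 entry rule only, exclude from the Week 16 count and from all later counts (AN and abscess) those lesions that were treated before Week 16 and recorded as no longer present at the Week 16 visit. Continue to count as present any treated lesion still there at Week 16 and any lesion treated at or after Week 16.

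State that this departs, for this analysis alone, from the counting rule in protocol 6.8.2.5 and SAP 2.4 and 6.6.1. Leave the Day 1-referenced endpoints unchanged. Report the as-written version as a sensitivity summary, with the number of subjects in whom m is 1 or 2.

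The cost is a paragraph of SAP text and an extra derivation; what sites record does not change. SAP Appendix 2 already uses a field named "How many lesions had intervention AND are no longer present". Before the wording is settled, check that the intervention fields identify lesion type and show status at the Week 16 visit. HiSCR needs abscesses counted separately, and the documents do not show that these fields allow it.

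### Flare and pain response in the SAP 6.6.7 placebo-switcher analyses mix Week 16 and Day 1 references: flares can only be lost, and pain response can be misjudged either way

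*SAP*

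**What the plan says.** The last block of SAP 6.6.7 covers subjects randomized to placebo who received at least one izokibep dose in Period 2 and had an AN count of at least "5 at Week 16 and HS lesions present in at least 2 distinct anatomic areas". Its stated purpose is "to address the question of how subjects respond to izokibep after 16 weeks of placebo, when they still meet original eligibility criteria".

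Two items in the list carry two reference points each:

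- **Flare after Week 16.** The item reads "HS flares from week 16 through 32, where HS flare is defined as proportion meeting the following two criteria". The first criterion is a rise of at least 25%, computed as "AN count at current visit- AN count at Week 16) / AN count at Week" 16. The second is "AN count at current visit- AN count at baseline ≥ 2". Both must be met.
- **Pain response at Weeks 24 and 32.** This is "at least 3 points reduction from baseline in NRS in Patient Global Assessment of Skin Pain at its worst, among subjects with Week 16 NRS" of 4 or more.

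Baseline cannot be read as Week 16 here. SAP 2.4 and 5.1.2 place it at or before randomization. The same list also treats the two as different: HiSCR is given once against Day 1 and once against Week 16, and Hurley Stage II is taken once at baseline and once at Week 16.

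**The concern.** Flare and pain change are meant to show what happens on izokibep from the point of the switch. A mixed reference lets the placebo period into the answer. A subject who improved on placebo and then worsened on izokibep may not register as a flare. A pain responder may owe the response to the first 16 weeks.

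The flare item looks like a definition only half adapted. SAP 2.5 and the protocol's Section 3 footnote state flare with both criteria on baseline. In 6.6.7 only the percentage criterion was moved to Week 16. The Week 16 version of HiSCR in the same list has all three of its components moved. The SAP gives no reason for a hybrid.

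At stake is whether these two rows answer the question the SAP sets for them.

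**Working it through.** The plan gives no figure for these items, so there is none to reproduce. The check applies each rule as written and compares it with the same rule referred wholly to Week 16.

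**Inputs**

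- D = AN at Day 1, at least 5 (Protocol 5.1, inclusion criterion 5).
- W = AN at Week 16, at least 5 (SAP 6.6.7, definition of this set).
- C = AN at a later visit. All three are whole numbers.
- Pain NRS runs from 0 to 10 (SAP 2.5).

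**Flare rules**

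- As written: (C − W)/W ≥ 0.25 and C − D ≥ 2.
- Both on Week 16: (C − W)/W ≥ 0.25 and C − W ≥ 2.

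**Step 1: on Week 16, the +2 criterion is always met.** With W ≥ 5, a 25% rise is at least 0.25 × 5 = 1.25 lesions, so at least 2 in whole counts. The Week 16 rule reduces to C ≥ 1.25W.

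**Step 2: the written rule adds nothing.** Every flare under the written rule already meets C ≥ 1.25W, so it is also a flare under the Week 16 rule.

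**Step 3: flares are lost only if AN fell on placebo.** If W ≥ D, then C − D ≥ C − W ≥ 2 and the two rules agree. If W < D, the lost counts are those with C ≥ 1.25W but C ≤ D + 1. A small fall may leave no such counts.

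| Day 1 | Week 16 | Lowest flare count as written (rise over Week 16) | Lowest, both on Week 16 | Counts lost |
|---|---|---|---|---|
| 20 | 10 | 22 (120%) | 13 | 13–21 |
| 12 | 8 | 14 (75%) | 10 | 10–13 |
| 10 | 8 | 12 (50%) | 10 | 10–11 |
| 10 | 9 | 12 (33%) | 12 | none |
| 10 | 10 | 13 (30%) | 13 | none |
| 8 | 12 | 15 (25%) | 15 | none |

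In the second row, the lost counts of 10 to 13 are 25% to 63% above Week 16 (10/8 = 1.25; 13/8 = 1.625).

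**Step 4: exhaustive check.** Over D and W from 5 to 60 and C from 0 to 120, the written rule drops 24,024 combinations that are flares on the Week 16 rule. It adds 0, and none of the dropped ones has W ≥ D. This confirms the logic. It is not a rate, because combinations are not equally likely.

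**Pain**

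| Day 1 | Week 16 | Later visit | Drop from Day 1 (as written) | Drop from Week 16 |
|---|---|---|---|---|
| 3 | 6 | 1 (Week 32) | 3 − 1 = 2: non-responder | 6 − 1 = 5: responder |
| 8 | 5 | 5 (Week 24) | 8 − 5 = 3: responder | 5 − 5 = 0: non-responder |

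A subject with a Day 1 score below 3 can never respond as written, because the scale stops at 0. Whole scores are used for simplicity. Under SAP 2.5 and 6.6.5 the Day 1 and Week 16 scores are averages of daily scores, which does not change the direction of either case.

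**Size of the set.** There are two placebo groups of 28–29, so 56–58 in all (170 × 2/6 = 56.7), before the Period 2 dosing and Week 16 disease conditions reduce it.

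**The case against.** **Only descriptive.** SAP 6.6 says that Period 2 in general carries no hypothesis tests, and these rows lie outside the testing sequence. That stands. It limits the importance of the point but does not make the definitions right.

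**Flare is defined only against baseline in the protocol, so Week 16 is not the true reference.** The documents do keep a wholly baseline-referenced flare through Week 32 in SAP 6.6.5. But the SAP itself chose Week 16 for the first criterion here and titles the item as flare from Week 16. The hybrid matches neither version.

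**The pain row may be deliberate.** The list keeps other Day 1 outcomes (HiSCR against Day 1; IHS4-55, defined from baseline in SAP 2.6). Total reduction since entry among subjects still in pain at the switch is a coherent summary, and a repeated-measures model later in the section also describes pain by visit. This stands in part: the row is computable and interpretable. It still does not measure response to izokibep after the switch, and the list offers no Week 16 responder row for pain as it does for HiSCR.

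**Stronger readings a reader might infer:**

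- *That the flare rule biases a comparison in favour of izokibep.* It can lower the flare proportion reported on izokibep, but everyone in this set has switched and there is no concurrent placebo group after Week 16. No drug-versus-placebo contrast is affected.
- *That a definite share of flares is lost.* Any such percentage depends on an assumed distribution of AN counts and of their change, and the documents give none.
- *That the pain rule simply understates response.* The second pain case shows the reverse.

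**Conclusion.** Both mixed references are in the current SAP text, and both should be corrected.

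For flare, the direction is certain: the written rule can only remove flares, and only in subjects whose AN count fell between Day 1 and Week 16. This rests on whole-number counts and the Week 16 entry condition of at least 5, and on no distributional assumption. For pain, the misclassification runs both ways, so the net direction is unknown.

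The size of either error cannot be stated from the documents. Its reach is small: two descriptive rows in at most about 57 placebo subjects. The primary and secondary tests and the HiSCR rows in the same list do not change.

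**What to change.** In the last block of SAP 6.6.7:

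1. **Flare, second criterion:** replace the reference to baseline with Week 16, so that the current AN count must exceed the Week 16 count by at least 2. In this set the criterion is then always met, but it keeps the usual two-part form.
2. **Pain response:** define it as a reduction of at least 3 points from Week 16 among subjects whose Week 16 score is 4 or more.
3. **If a Day 1 pain row is also wanted:** report it separately, with both the threshold and the drop on baseline, in the way HiSCR is already shown against each reference.

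The cost is two definitions and the matching table programs. No new data are needed, because the Week 16 AN counts and pain scores are already collected.
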